2 STUDY OVERVIEW

2.1 Study Objectives

2.1.1 Primary Objective

The primary objective is to evaluate the efficacy of LYR-210, compared with a sham procedure control, in improving the 3 cardinal symptoms (3CS) of Chronic Rhinosinusitis (CRS) in CRS participants without nasal polyps, who had previously failed medical management. The 3CS are nasal blockage/obstruction/congestion, anterior/posterior nasal discharge, and facial pain/pressure.

2.1.2 Secondary Objectives

The secondary objectives are to:

1. Evaluate the efficacy of LYR-210, compared with sham control, in improving the 3 cardinal symptoms of CRS in CRS participants without nasal polyps or with nasal polyps of grade 1, who had previously failed medical management.
2. Evaluate the efficacy of LYR-210, compared with sham control, in improving the individual CRS symptoms, CRS-related quality of life, the extent of inflammation in the ethmoid sinuses, and the need for rescue treatment in surgery naïve CRS participants without nasal polyps or with nasal polyps of Grade 1, who had previously failed medical management.

2.2 Study Design

2.2.1 Overview

This global, multicenter study will be conducted in a randomized, controlled, parallel-group, participant-blinded fashion in approximately 180 symptomatic adult CRS participants who have failed previous medical management. Participants enrolled in the study will include participants

[figure not shown]
who have accessible and intact middle meatuses. The efficacy and safety of LYR-210 matrix (7500 µg) versus a control group receiving a sham procedure will be assessed on a background therapy of daily saline irrigation. Participants will be randomized 2:1 to either treatment with LYR-210 or to control.

The study will consist of 3 stages:

- Screening and run-in stage: 2-4 weeks before randomization and treatment procedure
- Treatment stage (LYR-210 or control): randomization and treatment procedure through 24 weeks
- Safety extension: Weeks 25 through 52

A safety extension phase after the Week 24 visit will involve crossover to active treatment for control participants while treatment participants will be re-randomized 1:1 to either sham or a second round of active treatment with follow-up through Week 52.

Figure 1. Study Design.

2.2.2 Randomization and Blinding

On Day 1, after confirmation of eligibility and baseline assessments, and before any treatment, participants will be randomized in a 2:1 ratio to receive LYR-210 treatment or control (sham procedure) with stratification based on region (North America vs Europe) and nasal polyp status (yes vs no). Randomization will be conducted using Interactive Response Technology (IRT) and treatment will be assigned according to a randomization scheme generated by an unblinded biostatistician. The person generating the randomization scheme will not be involved in the collection, review, and/or analysis of study data before database lock and unblinding of the database.

To maintain the participant blind to treatment assignment, each participant will wear an eye mask (i.e., blindfold) and headphones at the time of the LYR-210 administration/sham procedure. Except for the cases of spontaneous matrix dislodgement, participants should remain blinded to their treatment assignment (LYR-210 or control) until the study is completed.

After Week 24, using IRT, control participants will be assigned to active treatment and treatment participants will be re-randomized 1:1 to either sham procedure or a second active treatment procedure stratified by geographic region and nasal polyp status at baseline. Follow-up visits will continue through Week 52.

The sponsor will be blinded to participants' initial study treatment assignments until database lock for the Week 24 primary analysis (initial randomized phase).

Due to the nature of the procedure, the treating investigator/surgeon will not be blinded to the treatment assignment. Efforts will be made to keep the study coordinator and other study staff blinded.

Breaking the blind to the participant is expressly forbidden except in the event of spontaneous dislodgment of LYR-210, or a medical emergency where the identity of the treatment assignment must be known to properly treat the participant. If breaking the blind is required because of a medical emergency, decision to unblind lies solely with the investigator. In all cases where the blind is broken to the participant, the investigator must record the date and reason for breaking the blind. The unblinding should be noted in the participant's electronic case report form (eCRF).

Every effort will be made to maintain the integrity of the study while conducting the 24-week analysis.

2.2.3 Study Drug

The LYR-210 System is a combination product comprised of a single-use applicator, preloaded with an anti-inflammatory drug matrix. LYR-210 contains mometasone furoate (MF), an active ingredient in multiple FDA-approved products indicated for therapeutic and prophylactic management of seasonal and perennial allergic rhinitis (AR), nasal polyps, a phenotype of CRS disease, and asthma. LYR-210 is designed to gradually soften over time and is made of bioabsorbable polymers that have been used as components of approved pharmaceutical drugs and/or medical devices.

Each LYR-210 contains a total MF dose of 7500 µg. LYR-210 is intended to be administered bilaterally into the middle meatus by an otolaryngologist under endoscopic visualization using the provided single-use applicator. Once administered, each LYR-210 is designed to gradually deliver sustained doses of MF to the inflamed mucosal tissue over a 24-week resident time. Bilateral placement of LYR-210 is designed to deliver a total dose of 15,000 µg MF over the 24 weeks, or an average daily dose of 89 µg MF per human participant (or approximately 45 µg MF per nostril).

On Day 1, participants who are assigned to the active treatment arm will have the LYR-210 administered bilaterally into the middle meatus according to the sponsor's instructions for use. Participants who are assigned to the control arm, will undergo mock administration (i.e., sham procedure)

After the procedure, all participants will be instructed to continue daily saline irrigation and completion of daily 4CS electronic patient-reported outcomes questionnaire (ePRO).

2.2.4 Sample Size Determination

Per the null and alternative hypotheses described in Section 3.1.6, 2:1 randomization (LYR-210:control), in the participants without polyps, [REDACTED]

With a sample size of 150 participants (n=50 control and n=100 LYR-210), alpha = 0.05, and power of 0.95, we will be able to detect an effect size of 0.63, which represents a mean difference of 1.31. This effect size is 18% smaller than the observed difference in the Phase 2 study (1.61 versus 1.31 3CS mean change scores). For the first key secondary endpoint (an analysis of the primary endpoint in all participants; n=60 control and n=120 LYR-210), the study will have 95% power to detect an effect size of 0.57, which represents a mean difference of 1.19.

2.3 Study Endpoints

2.3.1 Primary Efficacy Endpoint

The primary endpoint is the change from baseline (CFBL) in the 7-day average composite score of the 3CS of nasal blockage/obstruction/congestion, facial pain/pressure, and anterior/posterior nasal discharge at Week 24 in participants without nasal polyps at baseline.

2.3.2 Key Secondary Efficacy Endpoints

The key secondary efficacy endpoints.

1. CFBL in the 7-day average composite score of 3CS at Week 24 in all participants.
2. CFBL in the 22-item Sino-Nasal Outcome Test (SNOT-22) total score at Week 24 in all participants.
3. CFBL in the percent opacification of the bilateral anterior and posterior ethmoids at Week 20 as determined by 3-D volumetric CT analysis in all participants.
4. Rescue treatment (SCS for any reason/ESS) requirement through Week 24. (This endpoint will be descriptively summarized in this study and the statistical testing will be conducted on pooled data from this [ENLIGHTEN 1] study and the ENLIGHTEN 2 study)

The above key secondary and the below secondary endpoints will be analyzed for all participants.

If the primary efficacy endpoint is met, the key secondary endpoints will be tested, each at a 2-sided significance level of 0.05, using the hierarchical method in the above order.

2.3.3 Additional Secondary Efficacy Endpoints

Additional secondary endpoints include:

1. CFBL in 3CS score at Weeks 4, 8, 12, 16, and 20
2. CFBL in the symptom score for individual cardinal symptoms of nasal blockage/obstruction/congestion, anterior/posterior nasal discharge, and facial pain/pressure at Weeks 4, 8, 12, 16, 20, and 24
3. CFBL in loss of smell score at Weeks 4, 8, 12, 16, 20, and 24, for all participants and for participants with baseline score ≥ 2

4. Improvement of ≥ 1 point, ≥ 2 points, and ≥ 3 points from baseline in 3CS score at Week 24
5. CFBL in SNOT-22 total score at Weeks 4, 8, 12, 16, and 20
6. CFBL in SNOT-22 subdomain scores at Weeks 4, 8, 12, 16, 20, and 24
7. Improvement of ≥ 8.9 and ≥ 12 from baseline in SNOT-22 total score at Week 24
8. CFBL in the Zinreich score of the bilateral anterior and posterior ethmoids at Week 20
9. Time to first rescue treatment requirement through Week 24
10. Sinonasal surgery requirement through Week 24
11. Rescue medicine use through Week 24
12. Total systemic corticosteroids (SCS) dose prescribed through Week 24
13. Number of days on SCS through Week 24

16. CFBL in 36-Item short form health survey, version 2 (SF-36v2) physical health, mental health, and domain scores at Week 24
17. CFBL in EuroQoL 5-dimension, 5-level (EQ-5D-5L) score at Week 24
18. Improvement of ≥ 1 category and ≥ 2 categories in the severity of CRS-related symptoms as indicated by the Patient Global Impression of Severity (PGIS) at Week 24
19. Overall change of "very much better" or "much better" in the CRS-related symptom severity as indicated by the Patient Global Impression of Change (PGIC) at Week 24
20. CFBL in Medical Outcomes Study Sleep Scale (MOS Sleep-R) score at Week 24
21. CFBL in Work Productivity and Activity Impairment-Specific Health Problem (WPAI-SHP), version 2.0 at Weeks 4, 12, and 24

2.3.5 Safety Endpoints

Safety endpoints include:

1. Treatment-emergent adverse events (TEAEs) and treatment-emergent serious adverse events (TESAEs) through Week 24.
2. Abnormal (clinically significant) laboratory values (hematology and chemistry) through Week 24.
3. Newly identified adverse endoscopic findings in middle meatus including epistaxis, mucosal erosion or ulceration, and perforation through Week 24.
4. Clinically significant increase of intraocular pressure (IOP) through Week 24.
5. Newly identified or worsened cataract in one or both eyes by slit-lamp examination through Week 24.

3 STATISTICAL METHODOLOGY

3.1 General Considerations

The analysis for 24-week will include all data collected prior to the date of re-randomization. The analysis of AE will include all data collected prior to the date of successful insertion in the safety

extension. The analysis of clinical laboratory tests, nasal endoscopy, vital signs, and ophthalmologic assessments will include all data collected prior to and on the date of successful insertion in the safety extension.

3.1.1 Analysis Day

Analysis day for analysis visit windows (i.e., "Aday") will be calculated from the date of study treatment (LYR-210 or sham) administration. The day of study treatment administration will be Aday 1, and the day immediately before Aday 1 will be Aday -1.

3.1.2 Analysis Visits

Analysis visits will be used for efficacy and safety endpoint analysis.

For CS endpoints (3CS and 4 individual cardinal symptoms), analysis visits will be assigned according to the analysis windows specified in Table 1a. Analysis Visit Window for Weekly 3CS, 4 Individual Cardinal Symptom Scores, SNOT-22 [REDACTED] using daily CS weekly scores defined in section 3.1.4.3 and 3.1.4.4. The daily CS weekly score that is closest to the target day will be selected for analysis. If two daily CS weekly scores are equally distanced, select the value before the target day.

For other endpoints, scheduled visits will be assigned to analysis visits as recorded on the case report form (CRF) if they are within the corresponding analysis visit windows defined below. Scheduled visits that do not fall in the corresponding analysis visit windows are considered unscheduled visits when assigning analysis visits. In order to maximize the data available for assessments with regular scheduled visits, where possible, results from unscheduled visits will be assigned to analysis visits according to the following visit windows. When multiple visits are within the same analysis visit window, the one closest to the target day will be used. For efficacy endpoints, if two values are equally distanced, select the value before the target day. For safety endpoints, if two values are equally distanced, select the value after the target day.

If multiple ePRO are completed at the same day and the entry for individual questions is different, the entry having the worst score will be selected for analysis. Total score will then be calculated using selected worst individual scores. If multiple ePRO are completed at the same day and the entry for individual questions are identical, the earliest entry will be used for analysis.

3.1.2.2 Analysis Visit Windows for Safety Endpoints

For the subjects into safety extension, all days must be prior to re-randomization date in safety extension. For the subjects early discontinued from the treatment or completed the treatment stage but not into safety extension, all the follow-up data will be included for the Week-24 analysis using the windows below.

Table 1f. Analysis Visit Window for Laboratory and Slit-Lamp Examination Assessments

Analysis Visit	Target Analysis Day	Low Analysis Day	High Analysis Day
----------------	---------------------	------------------	-------------------

Week 24	169	85	210*
---------	-----	----	------

*The last day of the Week 24 is 6 weeks longer to minimize missing data at the Week 24 timepoint.

Table 1g. Analysis Visit Window for IOP Assessments

Analysis Visit	Target Analysis Day	Low Analysis Day	High Analysis Day
Week 8	57	36	63
Week 16	113	92	119
Week 24	169	148	210*

*The last day of the Week 24 is 6 weeks longer to minimize missing data at the Week 24 timepoint.

Table 1h. Analysis Visit Window for Nasal Endoscopy Assessments

Analysis Visit	Target Analysis Day	Low Analysis Day	High Analysis Day
Week 8	57	36	63
Week 16	113	64	119
Week 20	141	120	147
Week 24	169	148	210*

*The last day of the Week 24 is 6 weeks longer to minimize missing data at the Week 24 timepoint.

3.1.3 Definition of Baseline

For cardinal symptoms (3CS and individual symptoms), the baseline score is the average of non-missing daily scores over the 7-day period prior to and including Day 1. For other efficacy and safety assessments, the baseline value is the last non-missing value prior to or on the day of treatment administration.

3.1.4 Endpoint Related Definition and Calculation

3.1.4.1 Chronic Rhinosinusitis Cardinal Symptoms ePRO through Week 24

Enrolled participants will be asked to complete a daily ePRO questionnaire to assess the severity of the 4 individual cardinal symptoms of CRS (nasal blockage/obstruction/congestion, facial pain/pressure, anterior/posterior nasal discharge, and reduction/loss of smell). Each symptom is scored on a 0-3 scale as follows: 0 = none, 1 = mild, 2 = moderate, and 3 = severe.

3.1.4.2 Daily 3 Cardinal Symptoms Score

The daily 3CS score is the sum of the daily scores of the 3 cardinal symptoms (nasal blockage/obstruction/congestion, facial pain/pressure, and anterior/posterior nasal discharge). If any of the 3 daily scores is missing, the daily 3CS score for that day will be considered missing.

3.1.4.3 Individual Cardinal Symptoms Weekly Score

The nasal blockage/obstruction/congestion (or anterior/posterior nasal discharge or facial pain/pressure or reduction/loss of smell) weekly score for a day is the average of the non-missing daily scores over the 7-day period prior to and including that day. If less than 4 daily scores are available for a week, the individual CS weekly score will be considered missing for the week.

3.1.4.4 3 Cardinal Symptoms Weekly Score

The 3CS weekly score for a day is the average of the non-missing daily 3CS scores over the 7-day period prior to and including that day. If less than 4 daily 3CS scores are available for that week, the 3CS weekly score will be considered missing for that day.

For example, the 7-day average 3CS score at Day 57 can be interpreted as "the average 3CS scores in the daily score from Day 51 to Day 57 if at least 4 of them are non-missing".

3.1.4.5 SNOT-22

The SNOT-22 questionnaire is a 22-item disease-specific quality of life instrument validated for use in CRS. Each symptom is scored on a 6-point scale as follows: 0 = no problem, 1 = very mild problem, 2 = mild or slight problem, 3 = moderate problem, 4 = severe problem, 5 = problem as bad as it can be. The SNOT-22 total score is the sum of the 22 items and can range from 0 to 110 with higher scores indicating worse symptoms. The minimum clinically important difference (MCID) for the SNOT-22 total score has been determined to be 8.9 units. Additionally, the SNOT-22 scores can be divided into subcategories of rhinologic symptoms, extra-nasal rhinologic symptoms, ear/facial symptoms, psychological dysfunction, and sleep dysfunction. For each subcategory, the subdomain score is the sum of the items within that subcategory.

Table 2. Categorized survey items for separate domains of the SNOT-22 instrument

SNOT-22 Domains:	Survey Items:	Score Range:
Rhinologic Symptoms	#1, #2, #3, #6, #21, #22	0–30
Extra-Nasal Rhinologic Symptoms	#4, #5, #6	0–15
Ear/Facial Symptoms	#2, #7, #8, #9, #10	0–25
Psychological Dysfunction	#14, #15, #16, #17, #18, #19, #20	0–35
Sleep Dysfunction	#11, #12, #13, #14, #15	0–25

3.1.4.6 Sinus CT Scoring (Zinreich and 3-D Volumetric Scoring)

Opacification of the ethmoid sinuses will be assessed using CT images. Two scoring methodologies will be employed to assess sinus opacification - Zinreich modified Lund-Mackay and 3-D volumetric analysis.

The Zinreich modified Lund-Mackay scoring system uses a 0-5 scale for scoring each sinus. The scoring is based on the percentage of sinus opacification as follows: 0 = 0%, 1 = 1% to 25%, 2 = 26% to 50%, 3 = 51% to 75%, 4 = 76% to 99%, and 5 = 100% or completely occluded. The left and right sides are graded, and the sum is the total score out of maximum of 20.

3-D volumetric scoring will involve evaluations of each slice of 3-D coronal CT sequences and summing of all the slices to create a volumetric score ranging from 0% to 100%.

3.1.4.7 Time to first rescue treatment requirement through Week 24

Rescue treatment is defined as, after enrollment, participants receiving SCS for any reason, and/or recommended for sinonasal surgery to relieve CRS symptoms. See protocol section 3.4.3 for details.

Time to first rescue treatment requirement will be calculated from date of randomization, i.e., date of first rescue treatment requirement – date of successful insertion + 1. If a participant is lost to follow up/discontinues the study before Week 24 and does not have rescue treatment requirement by that time, then it will be censored at the date of last assessment. If a participant does not have rescue treatment required through Week 24, it will be censored at Week 24.

3.1.4.8 Rescue medication use through Week 24

The rescue medicine use through Week 24 is derived by checking whether the rescue medications are taken before Week 24, inclusive.

3.1.4.9 Sinonasal surgery requirement through Week 24

For participants who have a surgery or have a scheduled date for sinonasal surgery as rescue for CRS, the reason (worsening signs and/or symptoms during the study), the date the surgery was indicated, expected or actual surgery date, and the type and outcome of surgery will be recorded in the eCRF. Types of sinonasal surgery include, but are not limited to, functional endoscopic sinus surgery, balloon sinuplasty, turbinate reduction, septoplasty or polypectomy, or any endoscopic procedure that results in sinonasal tissue removal.

The study treatment will be discontinued and all procedures/assessments for the ET and end of treatment phase (EOTP) visits will be completed prior to the surgery. The participant will be discontinued from the study.

The sinonasal surgery requirement through Week 24 is derived by checking whether the sinonasal surgery is indicated before Week 24, inclusive. If a participant is lost to follow up/discontinues the study before Week 24 and does not have sinonasal surgery requirement at that time, this will be considered as a missing data for the analysis.

3.1.4.10 Total systemic corticosteroid (SCS) dose prescribed through Week 24

SCS for rescue treatment of CRS or for another reason that are prescribed to the participant are to be recorded in the eCRF.

If possible, an endoscopy should be performed before starting treatment with SCS. The participant should continue with the study treatment and follow-up visits per protocol. The investigator (or designee) will record the dates and dosing information (dosage form, daily dose, duration, name of drug) on the appropriate page(s) of the eCRF. Indication for SCS use will also be captured by selecting 1 or more of the following categories:

1. CRS
2. Asthma
3. Other respiratory or ENT disease (specify)
4. Other reason (specify).

A course of SCS is considered continuous if treatment is separated by less than 7 days.

The daily average will be calculated then multiplied by 168 days (24 weeks). If a participant is lost to follow up/discontinues the study before Week 24, the average calculation will be using the data from Day 1 to the last assessment date.

3.1.4.11 Number of days on SCS through Week 24

If a participant is lost to follow up/discontinues the study before Week 24 and does not have sinonasal surgery requirement at that time, the number of days on SCS will be calculated as

percent of days on SCS from Day 1 to the last assessment date multiplied by 168 days (24 weeks).

3.1.4.14 36-Item short form health survey, version 2 (SF-36v2) physical health, mental health, and domain scores

[figure not shown]
The SF-36v2 health survey captures participants' perceptions of their health and well-being in 8 dimensions: physical functioning, physical limitations, emotional limitations, social functioning, bodily pain, general health, and mental health. The items of the SF-36v2 are transformed and summed to a norm-based scale (mean=50, SD=10) for each physical and mental component domain in which higher scores indicate a better health-related quality of life status.

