- CFBL in the Zinreich score of the bilateral anterior and posterior ethmoids at Week 20
- CFBL in 36-Item short form health survey, version 2 (SF-36v2) physical health, mental health, and domain scores at Week 24
- CFBL in Medical Outcomes Study Sleep Scale (MOS Sleep-R) score at Week 24

The above endpoints will be analyzed by ANCOVA with fixed-effect terms for treatment group and nasal polyp status, and with baseline score as a covariate. LS-means in each treatment group and their difference with 95% confidence interval (CI) and p-value will be provided.

- Time to first rescue treatment requirement through Week 24

Time to first rescue treatment requirement through Week 24 will be analyzed using the Kaplan-Meier (K-M) method. The K-M estimate of median time to first recommendation of rescue treatment requirement with CI (if estimable) will be presented for each treatment group. Estimates of quartiles (25th and 75th percentiles) will also be presented for each treatment group. Time to first recommendation of rescue treatment will be compared between LYR-210 group and the sham procedure group using the log-rank test stratified by the stratification factor. P-value from the log-rank test will be presented.

- Total SCS dose prescribed through Week 24
- Number of days on SCS through Week 24

The above endpoints will be analyzed by ANCOVA with fixed-effect terms for treatment group and nasal polyp status. LS-means in each treatment group and their difference with 95% confidence interval (CI) and p-value will be provided.

Counts and percentages of subjects taking SCS medications by ATC class and preferred term will be summarized.

- CFBL in EuroQoL 5-dimension, 5-level (EQ-5D-5L) score at Week 24

The EQ-5D-5L descriptive system will be summarized as categorical variables by presenting the frequency and proportion of each level for each dimension by visit and by treatment arm, and analyzed by the Cochran–Mantel–Haenszel (CMH) test controlling for nasal polyp status and baseline score.

The overall health score on a 100-point vertical (visual analogue scale: 0 = worst imaginable health state; 100 = best imaginable health state) will be summarized as continuous variable and analyzed by ANCOVA including fixed-effect terms for treatment group and nasal polyp, and with baseline score as a covariate. LS-means in each treatment group and their difference with 95% confidence interval (CI) and p-value will be provided.

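### Scaling each dropout's systemic corticosteroid (SCS) dose or days up to 168 days lets one early-leaving SCS user dominate an arm mean in an unweighted ANCOVA, and the days rule is undefined for surgery dropouts

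*SAP*

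**What the plan says.** SAP 3.1.4.10 defines total SCS dose through Week 24 by a scaling rule: "The daily average will be calculated then multiplied by 168 days (24 weeks"). For a participant lost or discontinued before Week 24, "the average calculation will be using the data from Day 1 to the last assessment date".

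SAP 3.1.4.11 defines SCS days for dropouts as "percent of days on SCS from Day 1 to the last assessment date multiplied by 168 days (24 weeks"). It attaches a condition: the rule covers a dropout who "does not have sinonasal surgery requirement at that time, the number of days on SCS will be calculated as" above. It gives no rule for a dropout who does have a surgery requirement. The dose rule in 3.1.4.10 carries no such condition.

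SAP 3.4.3 analyses both endpoints together: "The above endpoints will be analyzed by ANCOVA with fixed-effect terms for treatment group and nasal polyp status". LS-means, their difference, a 95% CI and a p-value are reported. For these two endpoints the SAP states no minimum follow-up, cap, weight for follow-up time, transformation, count or rank model, or sensitivity analysis.

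Three related provisions matter. Protocol 3.4.3 describes rescue medication as a course of oral corticosteroids, and SAP 3.1.4.10 defines when a course counts as continuous. Under SAP 3.1.4.9, someone going to sinonasal surgery leaves the trial: "The participant will be discontinued from the study". Both endpoints are in the list of additional secondary endpoints (SAP 2.3.3, items 12 and 13), outside the fixed sequence in SAP 3.1.7.

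**The concern.** Dividing a short course by a short follow-up and multiplying by 168 treats the course as a steady daily rate that would have continued to Week 24. For episodic treatment this is not a reasonable prediction. A participant with one course who then leaves is recorded as if the course had recurred at the same density for the whole period. The ANCOVA gives that projected value the same weight as a value observed over 24 weeks.

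At stake are the LS-mean differences and p-values that describe how much steroid each arm needed. They can move appreciably because of when a single SCS user was last seen, with no additional steroid taken. The condition in 3.1.4.11 adds a second problem: the paired dose and days endpoints do not follow one rule for the same participant.

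**Working it through.** **Inputs from the documents.** Scaling to 168 days and the Day 1 to last-assessment denominator (SAP 3.1.4.10 and 3.1.4.11); ANCOVA with treatment and polyp status (SAP 3.4.3); arm sizes "n=60 control and n=120 LYR-210" (SAP 2.2.4); two-sided alpha 0.05 (SAP 3.1.6). The documents give no planning figure for the SCS endpoints, so there is none to reproduce.

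**Assumed inputs, not in the documents.** Course length (10 days; 5 to 14 tried), SCS use rates, and time of loss. Two-sample t-tests stand in for the ANCOVA; the polyp term is omitted.

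**1. Multiplier = 168 / days followed.**

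| Last assessment | Multiplier | A 10-day course becomes |
|---|---|---|
| Day 14 | 12.0 | 120 days |
| Day 28 | 6.0 | 60 days |
| Day 29 | 5.8 | 58 days |
| Day 57 | 2.95 | 29.5 days |
| Day 85 | 1.98 | 19.8 days |
| Day 141 | 1.19 | 11.9 days |

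For courses of 5 to 14 days, loss at Day 14 gives 60 to 168 days and loss at Day 28 gives 30 to 84. Dose scales by the same multipliers.

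**2. Share of the arm total from one such participant.** With k users in the arm, the share is scaled value / (10 × (k − 1) + scaled value). For example, sham with 10% use has k = 6, and loss at Day 14 gives 120 / (50 + 120) = 71%.

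| Arm, time of loss | 5% use | 10% use | 20% use |
|---|---|---|---|
| Sham (60), Day 14 | 86% | 71% | 52% |
| Sham (60), Day 28 | 75% | 55% | 35% |
| Sham (60), Day 85 | 50% | 28% | 15% |
| LYR-210 (120), Day 14 | 71% | 52% | 34% |
| LYR-210 (120), Day 28 | 55% | 35% | 21% |
| LYR-210 (120), Day 85 | 28% | 15% | 8% |

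**3. Effect on the comparison.** Take 12 of 60 sham and 12 of 120 LYR-210 users, 10 days each. Observed means are 120/60 = 2.00 and 120/120 = 1.00, so the difference is -1.00 day, p=0.063. Now one user is lost:

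| Loss at | In sham: difference, p | In LYR-210: difference, p |
|---|---|---|
| Day 14 | -2.83, 0.058 | -0.08, 0.96 |
| Day 28 | -1.83, 0.035 | -0.58, 0.50 |
| Day 57 | -1.32, 0.034 | -0.84, 0.18 |
| Day 85 | -1.16, 0.042 | -0.92, 0.11 |

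The steroid taken is identical in every row. At Day 14 in sham the difference nearly triples but p barely moves, because that one value also raises the sham SD from 4.0 to 15.7.

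**4. A person-time summary of the same data.** Sham, one user lost at Day 14: total days on SCS / total days followed × 168 = 120 / (59 × 168 + 14) × 168 = 2.03. The SAP rule gives (110 + 120) / 60 = 3.83; the observed mean is 2.00. With loss at Day 28 the three figures are 2.03, 2.83 and 2.00.

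**5. Behaviour over repeated trials (simulation).** Assumptions: one 10-day course per user, start times uniform; 8% dropout among non-users at uniform times; 20% dropout among users within two weeks of the course. With 30% sham versus 10% LYR-210 use, scaling moves the mean estimate from -2.0 to -2.6 days, power from about 0.91 to 0.76, and the pooled SD from 3.6 to 6.2. With equal use and equal dropout in both arms, the scaled test rejects about 4% to 5% of the time, so its size is kept.

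**The case against.** A reader might infer that the p-values for these endpoints are governed by dropout timing rather than steroid use, or that the rule produces false positives. The documents do not support that. A dropout with no SCS stays at zero, a completer is scaled by about 1, and only SCS users who leave early are distorted. When use and dropout are equal across arms, type I error is preserved.

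It is also fair to say that the factor of 12 is an extreme. The first scheduled post-procedure contact is Week 4, Day 29±3 (Protocol Table 4); a last assessment at Day 14 is possible through the daily ePRO but should not be taken as typical. SCS users are meant to stay in follow-up (Protocol 3.7.12). Surgery dropouts complete the ET and EOTP assessments first, and EOTP falls 25 to 31 days after ET (Protocol 3.5.8 and 3.7.13), which lengthens their follow-up. The 20% dropout among users in the simulation is assumed and drives its size.

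A further inference would be that 3.1.4.11 gives surgery dropouts a different value for the same steroid use. It does not say so; it leaves them without a rule. Wording close to this condition appears in 3.1.4.9, so a carry-over from there is plausible but unproven.

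Finally, steroid rescue is also assessed without extrapolation: time to first rescue with censoring, rescue medicine use by logistic regression, and counts of SCS users (SAP 3.1.4.7 and 3.4.3).

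All of this limits the size and reach of the problem. None of it supplies a cap, a minimum follow-up or a weight, and in the worked example even the roughly twofold multiplier at Day 85 takes p from 0.063 to 0.042.

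**Conclusion.** The rule is unsound as written for treatment given in courses. One SCS user who leaves early can dominate an arm mean, more easily in the smaller sham arm and when SCS use is low. In the 20% versus 10% example, one loss at Day 28 shifts the difference to -1.8 or -0.6 days depending only on the arm in which it falls. Across repeated trials the cost is precision and an inflated or distorted estimate, not a raised type I error under equal use and dropout. The multipliers follow directly from the SAP; every other magnitude rests on assumed course length, use rates and dropout times.

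Separately, the SCS-days rule is undefined for dropouts with a surgery requirement and does not match the dose rule. The primary and key secondary conclusions are unaffected. The change is worth making because it is cheap and these endpoints carry p-values.

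**What to change.** Remove the per-participant scaling to 168 days from SAP 3.1.4.10 and 3.1.4.11. Analyse observed SCS days and observed SCS dose over actual follow-up (Day 1 to Week 24 or last assessment) with a person-time method. A suitable choice is a log-link rate model with log follow-up as offset, treatment and polyp status as terms, and robust standard errors, since days and dose cluster within courses. Report the rate ratio or difference with its 95% CI. An offset still works on a rate scale, but short follow-up gets correspondingly little weight instead of being projected with full weight. A rank test on observed dose alone would not do the same job: it ignores unequal follow-up and gives no difference or CI.

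Present unscaled observed totals and follow-up time by arm alongside. Delete the surgery condition in 3.1.4.11 so that one rule covers every dropout for both endpoints.

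Cost: SAP wording and minor programming, with no new data. The headline summary becomes a rate comparison rather than an LS-mean 24-week total. The change should be made before the Week 24 database lock and unblinding, the point by which SAP section 1 requires approval.
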